Pharmacokinetics of Polymyxin B in Adult Patients with Cystic Fibrosis

NCT04335370

IRB Approval Date: December 4, 2019

Pharmacokinetics of Polymyxin B in Adult Patients with Cystic Fibrosis

Contents

1. Project Summary.....	2
2. Abbreviations.....	2
3. Background Information.....	2
4. Specific Aims / Hypothesis.....	4
5. Study Methodology.....	4
6. Data Analysis.....	9
7. Benefits and Risks.....	12
8. Adverse Events.....	13
9. References.....	14
10. Appendices.....	16

1. Project Summary

This is a single-center, open-label, non-interventional study to characterize the pharmacokinetics and safety of fixed-dose polymyxin B (PMB) in adult patients with cystic fibrosis (CF).

2. Abbreviations

ADL – activities of daily living

AKI – acute kidney injury

CF – cystic fibrosis

FEV1 – forced expiratory volume in 1 second

FiO₂ – fraction of inspired oxygen

GCS – Glasgow Coma Scale

KDIGO – Kidney Disease: Improving Global Outcomes

LC-MS/MS – liquid chromatography-tandem mass spectrometry

MDR – multidrug-resistant

NCI:CTCAE – National Cancer Institute: Common Terminology Criteria for Adverse Events

PK – pharmacokinetics

PMB – polymyxin B

Scr – serum creatinine

3. Background Information

Cystic fibrosis is a genetic disease affecting multiple organ systems; however, pulmonary disease is the cause of the majority of morbidity and mortality.¹ Pulmonary CF is a chronic, progressive disease process punctuated by episodes of acute exacerbation that require treatment. *Pseudomonas aeruginosa* is the predominant pathogen isolated in patients with acute exacerbations of cystic fibrosis, and guidelines from the Cystic Fibrosis Foundation recommend combination treatment directed against this pathogen as initial therapy.² Such therapy traditionally consists of an antipseudomonal beta-lactam with either an antipseudomonal fluoroquinolone or an aminoglycoside.

The demographics of patients with cystic fibrosis have shifted, and this shift has important implications for antimicrobial therapy. Once considered primarily a childhood disease, improvements in care have substantially increased the proportion of CF patients surviving into adulthood. In 1986, 70.8% of patients with CF were under 18 years of age. Data from 2016 CF Foundation Patient Registry Annual report show that the majority of patients currently living with CF are adults (52.7%) and that median survival is now well into middle age (47.7 years).¹ The prevalence of positive cultures for MDR *P. aeruginosa* is less than 10% in pediatric patients with CF, but increases steadily to around 20% in adults age 30-40 years.¹ This increase in drug-resistance over time likely reflects recurrent exposure to antipseudomonal antibiotics resulting in a severely limited armamentarium of active antibiotics to treat these patients into adulthood.

The polymyxins are cyclic peptide antibiotics which are positively charged at physiologic pH and exert bactericidal activity through binding to the lipopolysaccharide component of gram-negative bacterial membranes.³ Colistin, which is commercially available as the prodrug colistimethate sodium, has historically been the most commonly used polymyxin in patients with and without CF.^{4,5} There has been renewed interest into these compounds in the patients without CF due to the epidemic of antibiotic resistance. Population PK studies in critically ill patients have demonstrated high inter-patient variability in the exposure of formed colistin and inadequate attainment of therapeutic levels in patients with adequate or augmented renal function.^{6,7} The variability between patients in colistin exposure is due to variable conversion from colistimethate, which requires removal of five pro-drug functional groups, as

well as the differential pathways of elimination for colistimethate and formed colistin. Colistimethate is freely filtered and excreted in urine whereas formed colistin is avidly reabsorbed in the kidney and eliminated by non-renal mechanisms.⁸ The renal elimination of the inactive prodrug before conversion to the pharmacologically active form makes achieving colistin exposures associated with effective bacterial killing challenging in patients with adequate renal function. Patients with CF generally exhibit augmented clearance of renally eliminated compounds placing them at increased risk for underexposure.⁹ Polymyxin B, which is administered directly as active drug and reabsorbed in the kidney in a manner analogous to formed colistin, has demonstrated more consistent PK in critically ill patients.¹⁰⁻¹²

The impact of patient-specific variables on the PK of the polymyxins has been an area of active investigation. As highlighted above, patient renal function has a significant bearing on the PK of colistin, through its prodrug colistimethate sodium, but has negligible impact on polymyxin B.¹⁰⁻¹² Therefore, despite the fact that the polymyxin B label includes renal dose adjustments, this agent is dosed without respect to patient renal function in clinical practice.¹³ The only PK study of polymyxin B in patients with CF included 9 patients with only a median of 2 samples analyzed per patient (31 samples total).¹⁴ Interestingly, this study did identify a relationship between polymyxin B CL and creatinine clearance; however, the validity and magnitude of this relationship are uncertain given that most of the observed effect was due to a single patient. The other patient-specific factor which has traditionally informed the dosing of these agents is patient body weight. Population PK studies of colistin from the modern era of use have challenged the traditionally held belief that the clearance and volume of distribution scale with patient weight.^{6,7} In fact, the updated European Medicines Agency labeling for colistin recommends fixed-doses stratified by patient renal function based on these data.¹⁵ Similarly, the most recent PK studies of polymyxin B have failed to demonstrate an impact of patient body weight on the clearance of polymyxin B; however, the majority of polymyxin B dosing in clinical practice is still weight-based.^{11,12}

The polymyxins are associated with significant toxicities, namely, nephrotoxicity and neurotoxicity, which limit their clinical use. Therefore, it is important to assess the relative toxicity of colistin and PMB to ensure that shifting use to PMB for its PK advantages does not lead to increased toxicity. The comparative nephrotoxic potential of colistin and polymyxin B has been extensively investigated in non-CF populations, primarily the critically ill, and a meta-analysis of recent observational studies found an increased risk for acute kidney injury (AKI) with colistin relative to polymyxin B (RR 1.55, 95% CI 1.36-1.78).¹⁶ Only two studies assessing nephrotoxicity of both colistin and polymyxin B have included patients with CF. Phe and colleagues included 38 patients with CF and found that CF was actually protective against colistin associated AKI (aOR 0.03, 95% CI 0.001-0.79) in multivariable analysis.¹⁷ Unfortunately, no CF patients in this study received polymyxin B, so the relative rates of kidney injury between the two agents in this population could not be assessed. A 2017 study investigated the association between polymyxin treatment and kidney injury in 220 adult CF patients, 29 treated with PMB and 191 treated with colistin.¹⁸ The study found no difference in rates of AKI between PMB and colistin (34.5% vs 29.8%, p = 0.77) in patients nor in the rates of renal recovery by hospital discharge (90.0% vs 91.2%, p = 1.00). Neurotoxicity with the polymyxins are poorly characterized in patients with and without CF, especially with polymyxin B. Studies with colistin in pediatric patients with CF have found rates of neurotoxicity between 0 – 97.3% with many demonstrating higher rates of neurotoxicities than AKI.⁵ The most common manifestation of neurotoxicity with polymyxins is mild-moderate perioral paresthesia followed by weakness, ataxia, and in rare cases respiratory compromise.^{5,19,20} Neurotoxicity has not been evaluated in studies comparing colistin and PMB.

We propose to measure the plasma concentrations of PMB in adult patients with CF receiving intravenous therapy as a part of their routine care and to use these measured concentrations to build population pharmacokinetic models. The population pharmacokinetic modeling approach will allow the assessment of the impact of patient specific covariates (i.e. weight, renal function) on pharmacokinetic parameters. Patients will be monitored for nephrotoxicity and neurotoxicity to ensure that PMB has an acceptable

margin of safety in this patient population. This investigation will be the first to prospectively assess the pharmacokinetics and toxicities of PMB in this patient population and will facilitate optimal use of this compound in the management of acute pulmonary exacerbations of CF.

4. Specific Aim/Hypothesis

4.1. Measure the plasma concentration of PMB in adult CF patients receiving intravenous therapy. Adult patients with CF often receive multiple courses of antipseudomonal antibiotics over the course of their disease resulting in the evolution of multi-drug resistant (MDR) *P. aeruginosa* pulmonary colonizers. The polymyxins, colistin and PMB, frequently retain activity against MDR gram-negative bacteria. Colistin has historically been the most commonly used polymyxin in patients with CF; however, new pharmacokinetic (PK) and toxicity data obtained from non-CF populations suggest that PMB may achieve more consistent exposure with lower associated toxicity. We aim to measure concentrations of PMB in plasma samples obtained from adult CF patients treated with polymyxin B using liquid chromatography–tandem mass spectrometry (LC-MS/MS).

4.2. Characterize the pharmacokinetics of PMB in adult CF patients. There are three major population PK studies which inform the dosing of PMB and one small study including patients with CF. These studies suggest that the clearance of PMB is not related to patient body weight and have discordant results regarding patient renal function. Therefore, underweight patient populations with excellent renal function, such as CF, may be at risk for underdosing with traditional weight-based regimens. We aim to use population pharmacokinetic modeling to characterize the PK of fixed-dose PMB in this special population and assess the effect of patient-specific covariates (e.g., body weight, renal function) on PK parameters.

4.3. Determine the safety of PMB therapy in adult CF patients. Polymyxin use is limited to salvage therapy for MDR gram-negative bacterial infections and cases of allergy, intolerance, or adverse effects to alternative agents due to the significant toxicities related to these compounds. Nephrotoxicity is the most common dose-limiting toxicity; however, it has been poorly characterized with PMB in patients with CF. Neurotoxicity has also been reported and occurs with moderate frequency with colistin in studies of patients with CF. We aim to characterize PMB-associated nephrotoxicity using the Kidney Disease: Improving Global Outcomes (KDIGO) criteria and neurotoxicity via patient self-report.

5. Study Methodology

5.1. Study design: Single-center, open-label, non-interventional, pharmacokinetic study.

5.2. Inclusion criteria: Study subjects will be identified by investigators in the course of providing clinical care or by means of reports built in TheraDoc® Clinical Surveillance software (version 4.4; Premier Inc, Salt Lake City, UT) or built directly into the electronic medical record (EPIC Systems, Madison, WI). Subjects fulfilling the following criteria will be eligible for inclusion:

5.2.1. Adults, greater than 18 years of age

5.2.2. Diagnosed with cystic fibrosis

5.2.3. Treated with intravenous polymyxin B for a suspected or confirmed infection as part of routine care

5.3. Exclusion criteria

5.3.1. Extra-corporeal organ support systems that would alter drug distribution including renal replacement (e.g., hemodialysis, peritoneal dialysis, continuous renal replacement) or extra-corporeal membrane oxygenation

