5.3.2. Pregnancy

5.3.3. Unable to provide informed consent

5.4. Study Timeline

[figure not shown]

Figure 1: Study Timeline and Procedures. Abbreviations: CF, cystic fibrosis; LC-MS/MS, liquid chromatography tandem mass spectrometry, Scr, serum creatinine

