5.5. Informed Consent

5.5.1. Procedures: A member of the study team will review the study and informed consent with the potential participant and answer any questions. Written informed consent will be obtained from the patient prior to enrollment in the study. Informed consent documents will outline the risk associated with obtaining the blood samples as well as the anticipated benefits of the study. A copy of the signed informed consent will be given to the participant. Subjects will be free to opt out of the study at any time for any reason after enrollment.

5.5.2. Storage: Informed consent documents will be stored in a locked cabinet in a locked office. Copies of the informed consent documents will be uploaded onto M+Box with access restricted to IRB-authorized study personnel, and will also be uploaded to participant's medical record in MiChart.

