5.6. Dosing and Administration

5.6.1. The dose and duration of infusion for PMB will be determined at the discretion of the prescribing physician in the course of routine clinical care. There is no study intervention on the dosing and administration of PMB.

5.6.2. The recommended dosing schedule for intravenous polymyxin B at Michigan Medicine consists of an initial weight-based loading dose (2 mg/kg, maximum of 200 mg) followed by 100 mg every 12 hours for the duration of therapy as determined by the clinician. A reduction of the maintenance dose to 75 mg every 12 hours is recommended for patients with total body weight less than or equal to 50 kg.

5.7. Sampling:

5.7.1. Blood samples will be collected from enrolled patients at 5 time points during a single dosing interval under steady-state conditions. Sampling will occur on any day of therapy immediately prior to and following a single dose of PMB. The infusion time is selected at the discretion of the prescribing physician; thus the sampling schema is described based on the duration of infusion (Table 1).

Table 1: Sample collection times

Sample Code	Collection Timepoint	Collection Time Relative to Duration of Infusion (t_{inf})
C_0	Prior to Start of Infusion	0 hour
C_1	End of Infusion	$t_{inf} + 0$ hour
C_2	One Hour after End of Infusion	$t_{inf} + 1$ hour
C_3	Three Hours after End of Infusion	$t_{inf} + 3$ hours
C_4	Eight Hours	8 hours

5.7.2. Blood samples will be collected via one of three sampling methodologies: peripheral venipuncture, peripheral intravenous catheter, or a central venous catheter (e.g., PICC, Port). The method of obtaining blood samples will be determined by study personnel and will consider patient preference, patient safety, and the likelihood of obtaining adequate samples. Insertion of, care for, and sampling from indwelling catheters will be performed per hospital policy.

5.7.3. The procedure for obtaining and processing blood samples can be found in the Laboratory Protocol document in the Appendix (10.1).

5.8. Demographic and Clinical data: Study team members will obtain demographic and clinic data needed to describe the study population and build pharmacokinetic models. Data will be abstracted from DataDirect or obtained directly from the medical record for each index encounter. Data recorded directly from the medical record will be stored in REDcap.

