6.2. Toxicity Analysis

6.2.1. Nephrotoxicity: Nephrotoxicity will be assessed using the KDIGO criteria to define AKI. The nephrotoxicity endpoint will be met if subjects meet criteria for any stage of AKI by the KDIGO criteria using measured serum creatinine (Table 2). The degree of AKI will also be described by KDIGO stage. Time to renal recovery after cessation of PMB and the proportion of patients with renal recovery by hospital discharge will also be assessed. Renal recovery is defined as resolution of all KDIGO criteria for AKI.

Table 2: Definition of AKI using the KDIGO criteria

Stage	Serum Creatinine
1	1.5 – 1.9 x baseline OR ≥ 0.3 mg/dL increase from baseline
2	2.0 – 2.9 x baseline
3	≥ 3.0 x baseline OR

	$\geq 4 \text{ mg/dL}$ OR Initiation of renal replacement therapy
--	--

6.2.2. Neurotoxicity: Neurotoxicities will be assessed by patient self-report. The type of toxicity, anatomic site of toxicity, and severity will be assessed by the study personnel using the National Cancer Institute: Common Terminology Criteria for Adverse Events (NCI:CTCAE) scale.²⁵

Table 3: NCI:CTCAE terminology and definitions for potential neurotoxicities

CTCAE Term	Definition
Apnea	A disorder characterized by cessation of breathing
Ataxia	A disorder characterized by lack of coordination of muscle movements resulting in the impairment or inability to perform voluntary activities
Confusion	A disorder characterized by a lack of clear and orderly thought and behavior
Dizziness	A disorder characterized by a disturbing sensation of lightheadedness, unsteadiness, giddiness, spinning, or rocking
Dyspnea	A disorder characterized by an uncomfortable sensation of difficulty breathing
Hallucinations	A disorder characterized by a false sensory perception in the absence of an external stimulus
Hearing impairment	A disorder characterized by partial or complete loss of the ability to detect or understand sounds resulting from damage to ear structures
Muscle Weakness	A disorder characterized by a reduction in the strength of muscles in multiple anatomic sites
Paresthesia	A disorder characterized by functional disturbances of sensory neurons resulting in abnormal cutaneous sensations of tingling, numbness, pressure, cold, and/or warmth
Peripheral motor neuropathy	A disorder characterized by damage or dysfunction of peripheral motor nerves
Peripheral sensory neuropathy	A disorder characterized by damage or dysfunction of peripheral sensory nerves

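### Do the undated renal-replacement and consent exclusions distort the toxicity rates if patients enrol after their first polymyxin B dose?

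*Combined protocol and SAP*

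**What the plan says.** All references are to the combined protocol and SAP.

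- **Exclusions.** 5.3.1 removes patients on "Extra-corporeal organ support systems that would alter drug distribution including renal replacement"; 5.3.3 removes those "Unable to provide informed consent". Neither says when it is assessed relative to the first dose.
- **Entry.** 5.2.3 requires that the patient be "Treated with intravenous polymyxin B for a suspected or confirmed infection as part of routine care". Under 5.5.1, "Written informed consent will be obtained from the patient prior to enrollment in the study"; this fixes consent relative to enrolment, not to a day of therapy.
- **Sampling.** 5.7.1 states: "Blood samples will be collected from enrolled patients at 5 time points during a single dosing interval under steady-state conditions". It adds: "Sampling will occur on any day of therapy immediately prior to and following a single dose of PMB".
- **Outcomes.** Table 2 (6.2.1) lists "Initiation of renal replacement therapy" among the Stage 3 criteria. Table 3 (6.2.2) includes confusion, defined as "A disorder characterized by a lack of clear and orderly thought and behavior", and psychosis.
- **Summary.** 6.3.3 reports toxicity as counts and percentages, with no test, margin or decision rule.
- **Data.** 5.8 draws data for each index encounter. These include procedure codes for renal replacement (5.8.4) and serum creatinine (5.8.6).
- **Size.** The only statement of study size is the supply list in Appendix 10.1, which allows for at most 20 subjects.

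**The concern.** The same event bars a patient before enrolment and is a Stage 3 outcome after it, so the enrolment date decides whether it is counted. Nothing readable ties that date to the first dose. Steady-state sampling on any day of therapy means that doses have already been given by the time of sampling, so late enrolment is plausible.

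Three kinds of starter could then be missing from both numerator and denominator: those already on renal replacement, those who have lost capacity (possibly through a listed neurotoxicity), and those who have stopped the drug and can no longer be sampled around a steady-state dose.

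Aim 4.3 concerns safety, and 7.1.1 presents the data as a check on the safety of commonly used doses. If the worst cases were lost before enrolment, a report of no severe toxicity would look better than the experience of all starters. No planned count would show this.

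**Working it through.** **1. Study size.** Appendix 10.1 reproduces: 20 × 5 = 100 tubes; 100 × 2 = 200 cryovials; 200/81 = 2.5, so 3 boxes. I use n = 20 below. The plan gives no precision figure for Aim 4.3.

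**2. Is there a contradiction?** No. Read at enrolment, 5.3.1 bars patients already on renal replacement, and Table 2 counts those who start it later. Kidney injury without renal replacement, including Stage 3 by creatinine, is not excluded at all. For anyone enrolled, the 5.8 data can show creatinine changes before consent and renal replacement after it. Only patients who never enrol are at issue.

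**3. Effect of lost cases on a severe-event rate.** Suppose 0 of 20 enrolled patients have the event and k further starters were lost because of it (k is assumed). Exact Clopper-Pearson 95% intervals:

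| k | Rate | 95% CI |
|---|---|---|
| 0 | 0/20 = 0% | 0 to 16.8% |
| 1 | 1/21 = 4.8% | 0.1 to 23.8% |
| 2 | 2/22 = 9.1% | 1.1 to 29.2% |
| 3 | 3/23 = 13.0% | 2.8 to 33.6% |

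The first upper limit is 1 − 0.025^(1/20) = 16.8%. One lost case raises it by 23.8 − 16.8 = 7.0 points. All three point estimates lie inside the interval that 0/20 already carries.

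**4. How likely is a loss?** Let p be the share of starters who begin renal replacement before enrolment, and let every other starter enrol. The chance of losing at least one while 20 enrol is 1 − (1 − p)^20, and the expected number lost is 20p/(1 − p).

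| p (assumed) | Chance of at least one | Expected number |
|---|---|---|
| 0.5% | 9.5% | 0.10 |
| 1% | 18.2% | 0.20 |
| 2% | 33.2% | 0.41 |

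The documents give no value for p. They also give no rates of incapacity or early stopping, so those routes cannot be sized.

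**5. Does the denominator stay at 21?** Only if nobody declines. If, say, 10 starters without the event also declined (assumed), the rate among all starters would be 1/(21 + 10) = 3.2%, not 4.8%.

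**6. Any-stage kidney injury.** At a rate near the 34.5% cited in section 3, 7/20 = 35.0% would become 8/21 = 38.1% with one lost case. Unaffected starters who do not enrol pull the other way, so the net direction cannot be derived.

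**The case for a change.** The best case for a change is that it looks cheap. One sentence could date 5.3.1 at the first dose for the toxicity analysis, and one aggregate count could stand beside the 6.3.3 rates. If that count were zero, a finding of no severe toxicity would be easier to read, and reasons for non-enrolment are best logged as they arise.

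Part of this stands. The plan does not describe such a count, and the timing is not stated in readable text. A report that gave screened and non-enrolled numbers would be more informative.

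The remedies are weaker than they appear:

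- Dating 5.3.1 at the first dose creates toxicity-only participants in what 5.1 describes as a pharmacokinetic study, and it still cannot recover patients unable to consent.
- A count that includes everyone who stopped after the first dose would mix toxicity with completed courses and with stops for other reasons. 5.2.3 admits suspected infection, and 5.6.2 leaves duration to the clinician.
- The work involved goes beyond one sentence: it needs a screening log and possibly ethics-board wording for patients who did not consent.

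The incapacity route is also narrow. The lower grades of confusion and psychosis in Table 4 are mild or moderate and need not remove capacity. Section 3 describes polymyxin neurotoxicity mainly as mild to moderate paresthesia around the mouth.

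**Conclusion.** No change is needed. The text does leave the timing of 5.3.1 and 5.3.3 unstated, but analysts would fill this gap sensibly: eligibility is judged at enrolment, and the 6.3.3 percentages describe the patients who were enrolled. Read that way, nothing in the plan conflicts and nothing computed under it is wrong. Excluding patients on renal replacement is a fair trade-off for the pharmacokinetic aims, because it would alter drug distribution.

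The possible effect is modest: one lost case in about 20 shifts a zero rate to 4.8%, within the 16.8% upper limit that 0/20 already has. A study of this size could not support a claim of no severe toxicity with or without the extra count.

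This rests on three assumptions: that enrolment can follow the first dose, which Figure 1 may or may not limit; that about 20 patients enrol; and that few, if any, starters are lost in this way, which the documents can neither confirm nor rule out. If the report generalised from enrolled patients to all starters, that would be an overstatement in the report rather than a fault in the planned analysis.
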